## **8.0 STUDY DESIGN**

Prior to enrollment, patients referred for evaluation of an HSIL pap smear will undergo a full colposcopic evaluation, with biopsy confirmation. Clinical, histopathologic, virologic, and immunologic parameters will be assessed longitudinally in each study participant, as outlined below. The trial is a dose-escalation design, with a run-in cohort to assess the likelihood of mucosal irritation.

These serial assessments will directly parallel those obtained in the currently open CIN2/3 cohort study (JHMI JCCI# 99-08-27-04). Those patients who have measurable disease after biopsy will be eligible for study participation.

Cervical tissue specimens obtained as routine diagnostic and therapeutic specimens will be analyzed to characterize local tissue immune response. Diagnostic biopsies obtained at initial colposcopy will be used to confirm the diagnosis of CIN2/3. The initial diagnostic biopsy specimens will also be characterized in terms of type and quantitation of inflammatory cell infiltrates. Immunocytochemical techniques will be used to determine presence and numbers of macrophages, dendritic cells, T cells, B cells, and NK cells. We will also use standard staining techniques to detect cleaved caspase 3. As tissue availability permits, the specimens will also be analyzed for other immune cells. We will be comparing tissue profiles with those obtained on circulating PBLs in our study population. In the post-suppository administration, therapeutic LEEP/cone biopsy specimens, markers of local tissue immune response will be similarly characterized and quantitated. [name] will review all of the histologic slides.

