All unexpected and related SAEs will be reported immediately to [name], who will remove any at-risk patient from the study. Any subject who shows evidence of a drug-related SAE (grade III or IV) will be removed from the study and the SAE will be reported to the FDA and the JHMIRB within 7 working days of finding out.

Risks to privacy of individuals, confidentiality of data: There is a potential risk of loss of confidentiality. To ensure that all information and specimens collection remain

confidential and anonymous, all study data will be de-identified. Only the research team will have access to study participant private data. All study specimens are de-identified and cannot be linked to the subjects. Specimens will be barcoded before storage so that patient identifiers will not be available to the laboratories performing the assays proposed in this application.

To ensure that all study data remains confidential, all study data will be maintained on a password-protected database. Patient identifying information will not be associated with the study research data. Only the research investigators will be able to access a list connecting patient identifiers with the study ID, and this can only be provided upon special request from the study database managers.

The rate at which invasive cancer develops from CIN is slow and can take years and perhaps decades [49]. The fifteen-week treatment study window precedes the standard LEEP or cone excisional biopsy procedure given to the targeted study population, and therefore will not extend the normal time clinicians allow between disease detection and therapy and as such, participation in this study will not affect optimal patient treatment.

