## **12.0 STATISTICAL CONSIDERATIONS**

### **12.1 Study Design/Endpoints/Accrual**

The primary statistical outcome of the trial is safety. The treatment groups will be filled sequentially in a non-blinded manner. Study dropouts will be replaced.

The dose escalation algorithm is described as follows (see Table 4 for dose levels to be tested):

1. A run-in cohort of three patients will be treated with one 5-day cycle of 50mg vaginal suppositories. If no patient has a DLT observed by the cervix check visit after the last suppository, the trial will proceed to the next level.
2. A cohort of 9 patients will be enrolled and treated with one 5-day cycle of 200mg vaginal suppositories. If no patient has a DLT observed by the cervix check after the last suppository, the dose level will be considered tolerable and the trial will proceed to the next level.
3. If exactly one of the 9 patients has a DLT by Week 1-2 after the last suppository, three more patients will be enrolled and treated at the current dose level. If none of the three patients has a DLT by the cervix check after the last suppository, the current dose level will be considered safe and dose will be escalated.
4. If two or more of the 9 or 12 patients have a DLT observed by Week 1-2 cervix check, dose escalation will be stopped. The current dose level will be considered unsafe.
5. A cohort of 9 patients will be enrolled and treated with 2 cycles of 200 mg vaginal suppositories, at 2-week intervals. If no patient has a DLT observed in Cohorts II and III, then the dose level will be considered safe, and the dose will be escalated.
6. A cohort of 9 patients will be enrolled and treated with 3 cycles of 200 mg vaginal suppositories, at 2-week intervals. If no patient has a DLT observed by the cervix check after the last suppository, then the dose level will be considered safe.

With the dose escalation algorithm, there will be less than 9% probability to escalate to the next higher dose level if the DLT rate for the current dose level is 30%.

The maximum sample size for dose escalation is 39. Based on our experience in investigator-initiated therapeutic trials in this patient population at this institution, our anticipated accrual rate is 20-25 patients per year.

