At the end of dose escalation phase, one dose will be selected for the expansion phase from dose levels II-IV that are considered safe. In general, the lowest dose level with significant within subject decreases in viral load (from baseline at Week 15) and lesion clearance to CIN1 or less will be selected (see Section 12.2 for details). If none of the safe doses achieve significance for decrease in viral load and lesion clearance, a decision will be made based on the totality of safety and efficacy profiles of the dose levels considered safe.

A cohort of 12 patients will be enrolled and treated at the selected dose level at the expansion phase to further evaluate the safety and efficacy of Artesunate.

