## **12.2 Secondary Endpoints**

Secondary endpoints include change in histology (CIN2/3 or no CIN2/3) at week 15 and changes in cervical HPV viral load. These endpoints are chosen because in other trials they have been shown to be quantifiable and reproducible. They do reflect the biology of HPV infection and cervical intraepithelial disease, and furthermore have been shown to be modulated in response to intervention in other trials.[67] The histological outcome will be determined by comparing the initial diagnostic biopsy used for protocol entry with the exit cone resection. HPV viral load will be ascertained from longitudinally obtained cervical cell samples, using quantitative PCR.[68] This data will be used to estimate the regression rate within the fifteen-week window in the exploratory analysis.

Secondary endpoints will also include change in lesion size by colposcopy, and characterization of peripheral and local tissue response to the suppository. These measures will be correlated with clinical response, and with preclinical experimental data in the exploratory analysis. In every case possible, changes in lesion size by colposcopy will be ascertained by analyzing serially obtained digital colposcopic images. Measures of immune response will be ascertained on serially obtained peripheral blood specimens, and on flash frozen tissue from the therapeutic resection specimens.

To test that HPV viral load is different during and after treatment as compared to before treatment, paired t-tests and signed rank tests will be used. Log transformation (or other appropriate transform) will be performed to symmetrize the distributions and achieve normality. For each of these variables, a paired t-test will be performed. Due to the small sample size and potential non-normality of the data, the non-parametric signed rank test will also be used. The paired t-test tests whether or not the mean HPV viral loads at baseline and follow-up are

equivalent, whereas the Wilcoxon matched-pairs signed-ranks test tests whether the distributions of HPV viral loads is the same at baseline and follow-up.

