### 12.3 Other Efficacy Endpoints

[figure not shown]
In every case possible, change in lesion size from week 0 to week 15 will be measured using serial digital colpographs. Changes in HPV16 E7-specific T-cell response (CD8) will be compared at week 0 to week 15. Differences will be calculated between baseline and follow-up and the appropriate transform performed. Point estimates, confidence intervals, and hypothesis testing (i.e. paired t-test and signed rank test) will be done.

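### No masking to cohort or time point is described for the slide or colposcopic image readings, and the CIN1/CIN2 call is one of two parts of the expansion rule

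*Combined protocol and SAP*

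**What the plan says.** - **Allocation.** Section 12.1: "The treatment groups will be filled sequentially in a non-blinded manner". The three 200 mg cohorts differ only in the number of cycles: one, two or three.
- **Slides.** Section 8.0 assigns all of them to one reviewer, whose name is removed from the public text: "name] will review all of the histologic slides". The endpoint is binary. Sections 7.2 and 12.2 record CIN2/3 as present or absent at week 15, and Section 12.1 states the same cut as CIN1 or less.
- **Images.** Section 12.2: "changes in lesion size by colposcopy will be ascertained by analyzing serially obtained digital colposcopic images". Section 12.3: "change in lesion size from week 0 to week 15 will be measured using serial digital colpographs". Neither section says who does the measuring.
- **Use.** Section 12.1 selects for expansion "the lowest dose level with significant within subject decreases in viral load (from baseline at Week 15) and lesion clearance to CIN1 or less". If no safe level meets this, "a decision will be made based on the totality of safety and efficacy profiles of the dose levels considered safe".
- **Coding.** Section 10.1 labels specimens with a study ID for confidentiality. Section 11.5: "Specimens will be barcoded before storage so that patient identifiers will not be available to the laboratories".

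No section says whether the slide reviewer or the image reader is kept unaware of cohort, number of cycles or visit.

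**The concern.** Grading a lesion on either side of the CIN1/CIN2 line and outlining a lesion on a photograph are both judgements. If the reader knows, or can work out, how many cycles a woman received, an expectation that more cycles work better can tilt the borderline calls and suggest a trend across cohorts. If the image reader knows which picture is post-treatment, the same expectation can produce apparent shrinkage. Open-label dosing does not require open-label reading, so this is avoidable.

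At stake are the choice of expansion level and the secondary efficacy results. Colposcopic lesion size is an efficacy indicator (Sections 7.2 and 12.3). It is not named in the selection rule, but colposcopy touches histology indirectly: under Section 5.0 the week-15 view determines whether the tissue comes from a resection or from a biopsy of the original site.

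**Working it through.** **1. Is there any masking?** The plan gives no figure for reading error or reader agreement, so there is nothing of its own to reproduce; the provisions have to be compared. The two coding measures (Sections 10.1 and 11.5) are there for confidentiality. The first replaces names on labels. The second keeps identifiers from the assay laboratories. Neither mentions regimen, date, visit or the slide reviewer.

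**2. Does date carry information on cohort?** Section 12.1 expects 20 to 25 women a year. A cohort of nine then takes 9/25 × 12 = 4.3 months to 9/20 × 12 = 5.4 months to enrol, and the cohorts follow one another. Date therefore largely separates them. The separation is not perfect, because women removed before week 15 are replaced in their own cohort (Section 11.5) and a replacement may start late.

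**3. Sensitivity to one slide.** 1/9 = 11.1 points and 2/9 = 22.2 points. If a level grows to 12 after one DLT, 1/12 = 8.3 points. For scale, Section 5.0 gives spontaneous regression of 20-25% for HPV16 lesions and says that other genotypes regress more often.

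**4. Can one slide change a significance call?** Section 12.1 requires significance but names no test for clearance. I assume the Section 7.2 chi-square at p < 0.1, set against 250 comparison women (Section 12.4 says over 250), with a comparison rate of 20%, 22.5% or 25%.

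χ² = N(ad − bc)² / (product of the four margins), without continuity correction. At 20% (50/250):
- 3/9: 259 × (3×200 − 6×50)² / (9×250×53×206) = 0.949, p = 0.33
- 4/9: 259 × (4×200 − 5×50)² / (9×250×54×205) = 3.146, p = 0.076

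| Comparison rate | Change | p, uncorrected | Change | p, continuity-corrected |
|---|---|---|---|---|
| 20% | 3/9 to 4/9 | 0.33 to 0.076 | 4/9 to 5/9 | 0.175 to 0.032 |
| 22.5% | 4/9 to 5/9 | 0.124 to 0.021 | 4/9 to 5/9 | 0.255 to 0.057 |
| 25% | 4/9 to 5/9 | 0.184 to 0.038 | 4/9 to 5/9 | 0.348 to 0.092 |

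In every row one slide carries the level past 0.1.

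**5. Illustration with an assumed error rate.** Let m be the share of true non-regressors read as CIN1 or less. The documents give no value for m; I take 0, 5% and 10%. With true regression of 22.5%, the observed rate is 0.225 + 0.775m, and a level passes if at least 5 of 9 are read as regressed.

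| m | Observed rate | One level passes | At least one of three passes |
|---|---|---|---|
| 0 | 0.225 | 3.2% | 9.3% |
| 5% | 0.264 | 6.0% | 17.1% |
| 10% | 0.3025 | 10.2% | 27.6% |

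The last column is 1 − (1 − P)³ from unrounded P. For true rates of 20% to 25%, the one-level figure is 2.0-4.9% at m = 0 and 7.6-13.2% at m = 10%. These figures concern the histology component only. They are not chances of meeting the full rule, which also needs the viral-load result.

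**The case against.** The strongest reply is that this is an open-label Phase I trial with safety as its primary statistical outcome, a largely descriptive analysis and p ≤ 0.10 used only to flag ideas for later trials (Synopsis). Reading bias cannot reach the DLT counts or the escalation steps. That stands, and it limits the importance of the point.

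Viral load is a second, instrument-read requirement, so generous slide readings alone cannot satisfy the rule. That also stands. But the two parts are joined, so histology can still separate levels that all show a viral-load fall, and the fallback has no such check.

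A reader might infer more than the documents support:
- *That the slide reviewer also measures the images.* Section 8.0 covers histologic slides only, and Sections 12.2 and 12.3 name no image reader.
- *That images are analysed in visit order.* The wording in Section 12.2 describes how they are acquired, not how they are read.
- *That the study ID gives the cohort away.* No ID format is stated, and IDs are assigned at consent, before enrolment. Only the argument from date holds.
- *That readers are told the regimen.* The plan is silent. The reviewer's name is removed, so independence from treatment cannot be judged.

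Finally, masking within the trial leaves the comparison with the colposcopy database (Section 7.2) and the observational cohort (Section 12.4) unmasked. That is a real limit of the fix.

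**Conclusion.** The gap is real but modest. No masking to cohort or time point is described for the slides or the images, in a trial where specimen date can largely reveal the number of cycles. The slide call is one of two components of the expansion rule and part of the evidence for its fallback.

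It would go too far to say that these readings alone choose the level, or that lesion size enters the rule. The 11 points per slide reflect the granularity of nine women and would apply to any binary endpoint; they do not measure bias. The changes in p-value rest on an assumed test and comparator, and the pass probabilities on an assumed error rate. No estimate of actual bias can be drawn from the documents.

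The consequence is confined to secondary efficacy and level selection. I would treat masked reading as a cheap improvement, not as a defect in the trial's primary purpose.

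**What to change.** Add to Sections 8.0 and 12.2, for the endpoint reading only and with clinical care unchanged:

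- The existing slide reviewer reads the slides in one batch once the last escalation cohort has reached week 15. Slides carry non-sequential codes and are shuffled across cohorts, with regimen, dates, colposcopy and HPV results withheld.
- Whoever measures the colposcopic images does so with both cohort and visit hidden.
- These masked readings are the ones used in Sections 12.1 to 12.4.

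The timing fits, because selection follows escalation and already depends on week-15 data. No extra staff, procedure or patient is needed.

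Costs and limits to state openly:
- Relabelling and reading time.
- Occasional disagreement between the clinical and the endpoint reading.
- Possible recall, since the same person may have seen the slides before.
- Biopsy and excision slides remain distinguishable, so histology is masked to cohort but not to time point.
- Treated and historical-cohort slides are not masked against each other, so the same grading criteria must be kept for that comparison.

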## **9.0 STUDY POPULATION AND ENROLLMENT**

Patients with high-grade cervical intraepithelial lesions (CIN2/3) will participate in this study. At Johns Hopkins, patients will be recruited from the Johns Hopkins Colposcopy Service, and from referring physicians. Annually, the Colposcopy Service treats over 800 patients, approximately 15% of whom have high-grade lesions. In terms of feasibility, over the past 12 years we have recruited nearly 500 patients for screening to our cohort and vaccine studies, which consists of the same study population as the one described for this interventional trial. Of the HSIL patients approached for study entry, 80% have consented for screening. Of the patients who consented for screening, 33% were African American. This percentage is representative of our colposcopy population. It is anticipated that as therapeutic options become available through the upcoming Phase I trial, that referral volume will continue to increase.

### **9.1 Subject Inclusion Criteria**

- \* Patients with high-grade cervical intraepithelial lesions (CIN2/3) confirmed by colposcopy and biopsy.
- \* Patients who have measurable disease after diagnostic biopsy.
- \* Patients who weigh  $\geq 50$  kg
- \* Patients who are HPV-positive by DNA test
- \* Patients who are age 18 or older.
- \* Patients who are able to give informed consent.
- \* Patients who are immunocompetent.
- \* Patients who are not pregnant; committed to using adequate contraception through week 15 if of childbearing age. Condom use will be encouraged.
- \* Patients who have the ability to collaborate planned follow-up

### **9.2 Subject Exclusion Criteria**

- \* Patients with cytologic evidence of glandular dysplasia
- \* Patients with cytologic evidence of adenocarcinoma in situ

- \* Patients who are taking immunosuppressive medication
- \* Patients with concurrent malignancy except for nonmelanoma skin lesions
- \* Patients who have an active autoimmune disease or history of autoimmune disease requiring medical treatment with systemic immunosuppressants, including: inflammatory bowel disease, systemic vasculitis, scleroderma, psoriasis, multiple sclerosis, hemolytic anemic, or immune thrombocytopenia, rheumatoid arthritis, SLE, and Sjogren's syndrome, sarcoidosis. Asthma or COPD that does not require systemic corticosteroids or routine use of inhaled steroids is acceptable

## **10.0 STUDY PROCEDURES**

### **10.1 Screening**

[figure not shown]
All subjects will receive medical care that is routine to clinical practice.

Drs. [name] (JHU) and [name] (GBMC) and the study nurses or coordinators will recruit patients at the time they are seen for their initial clinical evaluation, or when they return to discuss their colposcopy results. All eligible patients will be asked if they would like to be screened for participation in this clinical trial. Drs. [name] and [name] and the study nurses or coordinators will be responsible for recruiting study participants and for obtaining written informed consent. They will allow as much time as necessary to review the consent forms with subjects, and to allow them to ask questions. Participants will receive a copy of the consent form at the time of their appointment, and consented subjects will undergo the procedures listed in Table 3 below.

Once patients sign consent, will be assigned a study ID, and their demographic and clinical information will be entered in the Cervical Dysplasia Research Program database. This information is also entered in the institutional database CRMS. To maintain confidentiality, the study-specific ID will be used to label all specimens collected and banked during the study. Only the clinical team and program manager will have access to PHI. All other members of the research team will only have access to study-specific IDs.

A schema of the data flow is outlined in Figure 1 below.

Figure 1: Data Flow Diagram

**Table 3: Outline of Evaluation Procedures**

	-3wks	Wk 0	Wk 2 	Wk 4 	Wk 6	Wk 15	Postop **	Wk 28	Wk 41
Informed consent	X								
Artesunate dosing		X	X	X					
Vital signs	X	X	X	X	X	X	X	X	X
Cervix check			X	X	X	X			
Medical history	X								
History of disease	X								
Demographic data	X								
Diary cards (give to pt)		X	X	X		X			
Diary cards (collect from pt)			X	X		X			
Adverse events		X	X	X	X	X	X	X	X
Inclusion/exclusion criteria	X								
Colposcopy	X				X	X		X	(X)*
Pap smear	X				X	X		X	X
HPV genotyping	X				X	X		X	X
Cervical swabs	X	X	X	X	X	X	X	X	X
LEEP/Cone**						(x)		(x)	
HLA testing ***	X								
PBL for banking****	X	(X)			X	X	X	X	X
Urine HCG	X	X	X	X		X			
Optional pheresis*****									

1. Treatment Group III

2. Treatment Group IV

\* Colposcopy only if clinically-required at wk 41

\*\* if residual disease is present (the procedure can happen any time after week 15, based on the physician's clinical judgment). The Postoperative visit will take place 4 +/- 1 weeks after the LEEP/Cone procedure.

\*\*\* HLA can be done at any time during the study, not an eligibility criterion

\*\*\*\* First blood draw can be done at either the screening visit or Wk 0, prior to dosing

\*\*\*\*\* pheresis is optional and can happen any time after week 15

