#### **5.0 RATIONALE FOR CLINICAL TRIAL DESIGN**

This trial is a prospective, open, dose-escalation study of topical Artesunate, formulated as a suppository, administered intravaginally, prior to standard therapeutic resection of the squamocolumnar junction at study week 15. An initial dose cohort of 3 subjects will receive intravaginal Artesunate for one 5-day treatment cycle. Based on clinical experience with Artesunate, we expect that absorption in the cervical mucosa, which is stratified squamous epithelium, will be less than what is observed with rectal administration, which is a single layer of glandular epithelium. Because cervical stroma is much less vascularized than colorectal stroma, we also expect significantly lower systemic levels of Artesunate in subjects receiving intravaginal dosing. The goal of topical administration is to achieve local, mucosal distribution of study drug, as opposed to systemic levels.

If we do not observe untoward side effects, including mucosal excoriation, in the first dose cohort, we will proceed with dose-escalation. The subsequent cohort will undergo two cycles of treatment, spaced at 2-week intervals. The final cohort will undergo a total of three cycles of treatment, spaced at 2-week intervals. All subjects will undergo an interval colposcopic exam at study week 6. At week 15, if there is still a colposcopically detectable lesion, subjects will undergo standard therapeutic resection. If no lesion is obvious, a biopsy will be taken at the site of the original lesion. The cohort receiving the fewest cycles of Artesunate, and showing therapeutic effect will be expanded (see Section 12 for details). At each vaginal exam, cervical swabs will be obtained and cryopreserved. Peripheral blood will be obtained by venipuncture at baseline, and at study weeks 5, 15, and 28, 41, and the postop visit, and will be cryopreserved for assessment of biomarkers.

This clinical cohort, healthy subjects with colposcopically-directed, biopsy-confirmed CIN2/3, was selected for safety reasons. The study protocol window (15 weeks), is within the standard of care. In pregnant women who have a cervical HSIL, the standard of care is to follow colposcopically until postpartum [7]. We and others have reported that the probability that CIN2/3 will progress in this timeframe is essentially zero [63]. In fact,

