**Table 4 – Treatment Cohorts**

Cohort	Number of patients	Dose	Treatment cycles
I	3	50 mg	1 (5 days)
II	9	200 mg	1 (5 days)
III	9	200 mg	2 (5 days each)
IV	9	200 mg	3 (5 days each)

In cohort I, at the first study visit, the subjects will be given a total of five suppositories and applicators. The first suppository will be inserted in clinic, by the patient. Patients will be given diary cards, and will return 1-2 weeks after completing the regimen, for visual assessment of the cervicovaginal mucosa.

In cohorts II-IV, the first study visit will be the same as the first study visit for the run-in cohort. Subjects will return to clinic 1-2 weeks later for visual assessment of the cervicovaginal mucosa. At study week 2, patients enrolled in cohorts III and IV will undergo a visual assessment of their cervicovaginal mucosa and will be given an additional 5 suppositories and applicators. Patients enrolled in cohort III will return to clinic 1-2 weeks later for visual assessment of the cervicovaginal mucosa. At study week 4, subjects enrolled in cohort IV will undergo a visual assessment of their cervicovaginal mucosa, and will also be given five suppositories and applicators. At study week 6, **all subjects** will undergo an interval colposcopic assessment. If their lesions do not appear to be more severe than at study entry, they will return at study week 15. At study weeks 15 and 28, all subjects will undergo colposcopic evaluation. If there is any residual colposcopically abnormal tissue, it will be removed using standard excisional procedures. Peripheral blood and cervical brush specimens will be obtained at study entry, at week 5, at week 15, and at the follow-up visits: postoperative visit, and at weeks 28 and 41.

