### **LEEP/Cone Excisional Biopsy Procedure**

After week 15, if there is residual colposcopic disease, the affected area will be excised using standard LEEP or cold knife cone technique. The resection specimens will be taken fresh to surgical pathology. Frozen section will be performed to confirm the presence or absence of CIN2/3. The frozen section block will be banked at  $-70^{\circ}\text{C}$ , and a sliver of tissue immediately facing the frozen section will be reserved for isolation of immune cells. This will allow unhampered routine diagnostic ability as well as preserve tissue sections frozen for characterization of inflammatory cell infiltrates. Routinely processed formalin-fixed, paraffin-embedded sections will also be analyzed for the characterization and quantitation of tissue infiltrates.

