### 12.4 Additional exploratory analysis

In addition to hypothesis testing, we will characterize the change in HPV viral load over the course of the trial using longitudinal data modeling. For each individual, we will have data on HPV viral load at weeks -2 (Screening visit), 9-10, and 15. A random effects model will be used to model the distribution of HPV viral load over time:

$$hpv_{it} = \beta_{0i} + \beta_1 t + \beta_2 t^2 + \varepsilon_{it}$$

where  $hpv_{it}$  is individual  $i$ 's HPV viral load at week  $t$ . Correlations between observations within an individual are accounted for by the random intercept (i.e. random effect) term. A quadratic model is used to account for non-linearity in the change of HPV viral load. From the fitted model, we can estimate the effect of the vaccine treatment on viral load. The plot below is based on simulated data and shows the type of result we hypothesize: a downward trend in HPV viral load that flattens as time increases. Based on the random effects model shown above, we can estimate the average response (denoted by the thick line) and better understand the association between the vaccine and response and specifically when changes in viral load tend to occur.

Lesion size will also be described using the random effects linear longitudinal model described above to look for time trends.

The secondary efficacy endpoints will be compared with analogous data obtained in a currently open cohort study, “Evaluation of Tissue and Peripheral Blood Immune Response in Women with HPV16+ Cervical Intraepithelial Lesions” (Johns Hopkins IRB# NA\_00037578). This observational cohort protocol has been open since 1999, and currently includes over 250 subjects. These subjects have the same eligibility criteria as the criteria for this trial, and are followed prospectively for the same timeframe, before undergoing standard therapeutic resection at week 15. To date, no CIN2/3 lesions have progressed to invasive disease in this timeframe, which is well within the standard of care. We will compare changes in HPV viral load and lesion size from baseline at Week 15, rates of histologic regression, and change in viral load over the 15 week window, in both cohorts.

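### The week-15 histologic regression rate rests on an excision specimen with no latest date, so natural regression after week 15 can be counted in the drug's favour

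*Combined protocol and SAP*

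**What the plan says.** The sections differ on when excision happens.

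- Section 5: "At week 15, if there is still a colposcopically detectable lesion, subjects will undergo standard therapeutic resection". For women without a visible lesion it adds: "If no lesion is obvious, a biopsy will be taken at the site of the original lesion".
- Section 7.2 judges histologic regression on a resection specimen labelled week 15.
- Table 3 (Section 10.1) marks LEEP/cone under both week 15 and week 28. Its footnote, which applies if residual disease is present, says that "the procedure can happen any time after week 15, based on" clinical judgement.
- Section 10.4: "After week 15, if there is residual colposcopic disease, the affected area will be excised using standard LEEP or cold knife cone technique". No upper limit is given.
- Section 10.3: "At study weeks 15 and 28, all subjects will undergo colposcopic evaluation", with any residual abnormal tissue then removed.
- Section 10.2 allows ± 1 week around the week-15 visit. It gives no window for the excision.

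Section 12.2 names histology at week 15 as a secondary endpoint and determines it by comparing the entry biopsy with the exit cone, whose date is not restricted. Of the histology and viral load data it says: "This data will be used to estimate the regression rate within the fifteen-week window in the exploratory analysis". Section 12.4 compares rates of histologic regression with an observational cohort followed "before undergoing standard therapeutic resection at week 15".

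**The concern.** The protocol itself says these lesions regress without treatment (Section 5), so the time allowed before tissue is taken is part of what a regression rate means. Only women who still have a visible lesion at week 15 can have their excision deferred. During the delay, natural regression can turn a woman who had not regressed at week 15 into one with no CIN2/3 in her specimen. If that specimen feeds the week-15 rate, the treated group gains time that the comparison cohort, as described, does not have.

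Two uses of the rate are exposed: the estimate of regression within fifteen weeks, and the comparison with untreated women as an indicator of drug efficacy (Sections 7.2 and 12.4). Lesion clearance to CIN1 or less also enters the choice of expansion level in Section 12.1, though less directly.

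**Working it through.** The plan states no power, error rate or expected value for the histologic comparison, so there is no figure of its own to reproduce. What follows is an illustration of size.

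**Inputs from the protocol**
- Natural regression in the study window: 20-25% for HPV16 lesions (Section 5). Other genotypes are said to regress more often.
- Comparison cohort: over 250 women (Section 12.4).
- Efficacy signal: chi-square test, p < 0.1 (Section 7.2).
- Patients at 200 mg: 9 + 9 + 9 = 27 (Table 4).

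**Assumptions not in the protocol**
- Regression occurs at a constant hazard and the drug is inert.
- Women who have regressed by week 15 have no visible lesion then and are unaffected.
- A share f of the remaining women is deferred to week T. Both f and T are unknown; week 19 stands for a short delay and week 28 for a long one.

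**Formulas.** With r the regression rate by week 15, the rate by week T is p(T) = 1 − (1 − r)^(T/15). The apparent week-15 rate is r + f × (p(T) − r).

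**Numbers**
- p(19) = 1 − 0.80^(19/15) = 0.246 and 1 − 0.75^(19/15) = 0.305.
- p(28) = 1 − 0.80^(28/15) = 0.341 and 1 − 0.75^(28/15) = 0.416.
- A quarter deferred to week 28: 0.20 + 0.25 × 0.1407 = 0.235 and 0.25 + 0.25 × 0.1655 = 0.291.

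| Share of visible lesions deferred | Deferred to | Apparent rate, r = 20% | Apparent rate, r = 25% |
|---|---|---|---|
| None | – | 20.0% | 25.0% |
| A quarter | week 28 | 23.5% | 29.1% |
| Half | week 28 | 27.0% | 33.3% |
| All | week 19 | 24.6% | 30.5% |
| All | week 28 | 34.1% | 41.6% |

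Starting the clock at the screening biopsy (18 weeks before week 15) lowers the last row to 31.9-39.1%.

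**Chance of a false favourable signal.** This was computed by exact enumeration of the Pearson chi-square test without continuity correction, for 27 treated women against an assumed 250 controls whose true rate is r. It is 5-6% with no deferral, 13% with a quarter deferred to week 28, and 51-57% with all deferred to week 28.

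**The case against.** The strongest reply is that the plan already ties the endpoint to week 15. The objectives, Section 7.2 and the opening of Section 12.2 all say so, and on those words a week-28 specimen does not qualify. A reader might infer that a woman excised at week 28 will be scored as a week-15 regression. The documents do not say that. It is one reading of conflicting text, because the specimen named in Section 12.2 carries no date limit and no rule covers a late one.

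The week-28 mark in Table 3 and the sentence in Section 10.3 may refer only to disease found at week 28. Table 3 also places the postoperative visit, 4 ± 1 weeks after excision, between weeks 15 and 28, which suits excision near week 15. That stands. Open-ended timing therefore rests on the footnote and on Section 10.4, and both could be ordinary scheduling latitude.

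The comparison cohort's own protocol is not available. Section 12.4 describes its timing in one clause, and similar latitude may exist there.

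A reader might take 34-42% as the expected bias. It requires every visible lesion to be deferred by 13 weeks at a constant hazard, and nothing in the documents supports that. A reader might also infer that the choice of expansion level is distorted. Section 12.1 also uses viral load at week 15, and the same excision rule applies in every cohort, so no direction of bias between levels is shown.

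Finally, the endpoint is secondary, the rate estimate and cohort comparison are exploratory, and analysis is mainly descriptive. This limits the stakes but does not remove the gap.

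**Conclusion.** The concern holds in conditional form. The sections conflict on when excision happens, the endpoint specimen has no latest date, and no text says how a late specimen is handled. If excisions are deferred and those specimens are used, the error favours the drug.

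Its size is unknown. Under the stated assumptions it runs from about 4 percentage points (a quarter deferred to week 28) to 5-6 points (all to week 19), and to 14-17 points only in the extreme case. With no deferral it is zero. The primary safety outcome is unaffected, as are viral load and colposcopic lesion size measured at the week-15 visit. Because the remedy is mainly wording, the change is worth making even if deferral proves rare.

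**What to change.** In Sections 7.2 and 12.2:

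1. Define week-15 histology from tissue taken within the week-15 window, ± 1 week as in Section 10.2, whether by excision or by biopsy.
2. Record the study week of every excision. Report later specimens separately by that week, and do not count them as week-15 regressions.
3. Show the week-15 rate twice: with deferred visible lesions counted as not regressed, and with those women excluded. The first is the lowest value the rate can take. The second is an upper value only if deferred women had regressed by week 15 no more often than the rest.
4. State how to classify a woman resected early for progression under Section 11.9, since her tissue may also fall outside the window.

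In Section 12.4, apply the same cut-off to the comparison cohort by actual excision date.

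Section 5, the Table 3 footnote, Section 10.3 and Section 10.4 must be reconciled on the timing of excision. Which of them is right is a clinical matter on which this review takes no position.

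The cost is endpoint wording, one date field, and retrieval of excision dates for the comparison cohort. The downside is that some women will have no qualifying week-15 tissue, and counting them as not regressed may understate the rate where a visible lesion was already CIN1 or less.
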